15. PROCEDURE DESCRIPTION

15.1. Measurements and Evaluations, Cohorts 1, 2 and 3

15.1.2. Slit Lamp Biomicroscopy Exam Guidelines

Slit lamp biomicroscopy will be performed using the investigator's standard procedure. This procedure will be the same for all patients observed at an investigator's site. Observations should be graded as normal or abnormal. In the event of abnormal observations, all findings should be noted and specified as clinically significant or not clinically significant and graded on a 5 point scale (0 = None, 0.5 = Trace, 1.0 = Mild, 2.0 = Moderate, 3.0 = Severe). Observations for each eye should be made of the following variables:

• Eyelid erythema

- Confidential
 - Chemosis
 - Corneal Staining
 - Corneal edema
 - Corneal opacity (At Visit 2 (Baseline) and if corneal opacity is observed, please collect corneal photograph at each visit until opacity has resolved or patient is exited from the study at selected sites.)
 - Hyphema
 - Anterior synechiae
 - Posterior synechiae
 - Lens
 - Conjunctival hyperemia (Hyperemia should be evaluated on a seven point scale [0, 0.5, 1, 1.5, 2, 2.5, 3] against the provided Ora CalibraTM Redness Scale #6.0b. Findings should be noted as diffuse or injection site).
 - Conjunctiva (findings other than hyperemia)

Anterior Chamber Cells Grading Scale – evaluated against the SUN Scale (9)

0 = < 1 cell in field

.5+=1-5 cells in field

1+=6-15 cells in field

2+=16-25 cells in field

3+=26-50 cells in field

4+=50+ cells in field

Anterior Chamber Flare Grading Scale - evaluated against the SUN Scale (9)

0 = None

1+ = Faint

2+ = Moderate (Iris/lens details clear)

3+ = Marked (Iris/lens details hazy)

4+ = Intense (fibrin/plastic aqueous)

15.1.3. Corneal Staining

The cornea will be stained with non-preserved 2% fluorescein. When conducting all assessments room temperature and humidity should be relatively consistent throughout each visit and throughout the study. Observations should be graded as normal or abnormal. In the event of

abnormal observations, all findings should be noted and specified as clinically significant or not clinically significant and graded for severity on a 0-5 scale.

15.1.4. Binocular Indirect Ophthalmoscopy (Dilated Fundus Exam) Guidelines

Dilated ophthalmoscopy will be performed according to the investigator's preferred procedure. This procedure will be the same for all patients observed at an investigator's site. Observations should be graded as normal or abnormal. All findings should be noted and specified as clinically significant or not clinically significant and graded for severity on a 0 - 5 scale. The fundus will be examined thoroughly and the following variables examined:

- Retina
- Macula
- Choroid
- Vitreous
- Optic nerve/disc
- Cup/disc ratio

15.1.5. Body System Review

Abbreviated body system review examinations will be performed and include the following examinations.

- General appearance
- Skin
- Lymphatic
- Head and Neck
- Ears Nose and Throat
- Chest and Lungs
- Cardiovascular
- Abdomen
- Extremities
- Musculoskeletal
- Neuromuscular

15.1.6. Vital Signs

Vital sign assessments will include measurements of heart rate, blood pressure, and respiration rate.

15.1.7. Laboratory Safety Assessments and Systemic Exposure to Travoprost

Laboratory samples will be collected as indicated in the Times and Events schedules. Labs should be non-fasting however, if not, please indicate on the lab requisition form as well as in the patient's chart. Chemistry, hematology and urinalysis will be assessed according to the central laboratory procedures manual. A urine pregnancy test will be performed on all females of childbearing potential.

15.1.8. Anterior Chamber Optical Coherence Tomography (OCT)

Anterior chamber OCT images will be acquired per instructions provided in the OCT manual. Images will be evaluated for angle opening distance at a central reading center. Additional details about collection, handling and interpretation of images will be provided in the OCT manual. At least one collected anterior chamber OCT image should include the ENV515 implant(s) in the field of view at each visit.

15.1.9. Gonioscopy

Gonioscopy will be performed to grade the iridocorneal angle according to the Shaffer gonioscopy scale. Gonioscopy will also be used to monitor the implant location. The Shaffer scale should be used to describe the angle created between the plane of the iris and the cornea as follows:

- Grade 4: 35 to 45 degrees, wide open, closure improbable
- Grade 3: 20 to 35 degrees, moderately narrow, closure possible
- Grade 2: <20 degrees, extremely narrow, closure probable
- Grade 1: partly or totally closed, closure present

The orientation of the implants will need to be indicated on source documents for each patient. In Cohorts 2 and 3 select sites will collect gonioscopy images. If gonioscopy images are collected, please conduct the gonioscopy after the last IOP measurement. Photographs will be taken at visits post dose starting a Visit 5 and continue at visits until the patient is exited from the study.

15.1.10. Visual Field (Humphrey Program 24-2 SITA-Standard Strategy)

The VF assessment will be performed on the Humphrey Field Analyzer using the program 24-2. All VF examinations will be performed with the patient's best correction for 33 cm. The pupil should be at least 3 mm in diameter. If not, pharmacologic dilation should be used for VF testing. Quantified single threshold perimetry may be used if desired. Swedish Interactive Threshold Algorithms (SITA), Fastpac, or a similar program may be used. SITA Fast may not be used.

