 - If dilation is required to properly conduct BCVA (ETDRS) with manifest refraction, the assessment should be performed after the slit lamp biomicroscopy and IOP measurement.
- 2. Perform pupil measurement
- 3. Perform slit lamp biomicroscopy
- 4. Perform corneal staining
- 5. Measure IOP at 8:00 a.m. (±30 minutes)
 - IOP must be between 22-34 mm Hg in both eyes with a ≤4 mm Hg difference between each eye at 8:00 a.m. (± 30 minutes)
- 6. Perform gonioscopy
- 7. Perform pachymetry (contact)
- 8. Perform specular microscopy (non-contact)
 - Non-contact specular microscopy can be performed anytime during the site visit and does not need to follow the order as written.
- 9. Perform anterior chamber OCT
- 10. Perform physical examination (can be performed anytime during the site visit and does not need to follow the order as written)
- 11. Assess vital signs (can be performed anytime during the site visit and does not need to follow the order as written)
- 12. Collect non-fasting blood and urine for clinical laboratory tests
- 13. If female of childbearing potential, perform urine or serum pregnancy test
- 14. Measure IOP at 10:00 a.m. (±30 minutes)
 - IOP must be between 22-34 mm Hg in both eyes with a ≤4 mm Hg difference between each eye at 10:00 a.m. (± 30 minutes)
- 15. Measure IOP at 4:00 p.m. (\pm 30 minutes)
 - IOP must be between 19-34 mm Hg in both eyes with a ≤4 mm Hg difference between each eye at 4:00 p.m. (± 30 minutes)
- 16. Perform dilated funduscopic examination
- 17. Verify that patient meets all entry criteria

Patients are expected to remain in the clinic for the completion of all procedures (~8:00 a.m. to ~5:00 p.m.). However, at the discretion of the investigator, patients will be permitted to leave the clinic after completing the 10:00 a.m. IOP measurement and will return to the clinic before the 4:00 p.m. IOP measurement. Any patient that leaves the clinic will be instructed to return no later than 30 minutes prior to the 4:00 p.m. IOP measurement.

5.2.2. Patient Instructions, Cohort 1

Before patients leave the clinic, they should receive an appointment for their next study visit and the instructions provided in Section 5.1.2.

5.3. Visit 3/Day 1/Randomization/Treatment, Cohort 1

Query patient about changes in medications and whether or not they have experienced symptoms suggesting an AE. AEs will be documented.

5.3.1. Pre-dose Assessments, Cohort 1

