- 14. Collect non-fasting blood and urine for clinical laboratory tests **and** systemic PK only at **Visits 10, 11, and 13** for clinical laboratory tests and at all visits for systemic PK (can be performed after the 10 a.m. IOP)
- 15. Collect used timolol maleate 0.5% ophthalmic solution bottle and distribute new bottle to patient

Patients are expected to remain in the clinic for the completion of all procedures (\sim 7:30 a.m. to \sim 5:00 p.m.). However, at the discretion of the investigator, patients will be permitted to leave the clinic after completing the 10:00 a.m. IOP measurement and will return to the clinic before the 4:00 p.m. IOP measurement. Any patient that leaves the clinic will be instructed to return no later than 30 minutes prior to the 4:00 p.m. IOP measurement.

Before patients leave the clinic, they should receive an appointment for their next study visit and the instructions provided in Section 12.3.4.

12.10. Visit 16/Month 12 ± 7 Days/Treatment Period Study Exit, Cohort 2 (if patient chooses not to enroll in Extension 1)

If a patient discontinues prior to the Visit 16/Month 12, or declines to continue into the Cohort 2 Study Extension 1 and chooses to exit the study at Visit 16/Month 12, the following procedures are to the performed. If the patient chooses to continue into the Cohort 2 Study Extension 1, please follow the procedures in Section 12.11.

Query patient about changes in concomitant medications and whether or not they have experienced symptoms suggesting an AE. AEs will be documented.

- 1. Assess BCVA (ETDRS) with manifest refraction
- 2. Perform pupil measurement
- 3. Perform slit lamp biomicroscopy
- 4. Perform corneal staining
- 5. Measure IOP at 8 am (±30 minutes, please make sure that timolol maleate 0.5% ophthalmic solution is administered after the IOP measurement)

- 6. Perform gonioscopy (if gonioscopy images are collected, please conduct the gonioscopy after the 4:00 p.m. IOP measurement)
- 7. Perform pachymetry (contact)
- 8. Perform specular microscopy (non-contact) for both eyes (can be performed anytime during the visit)
- 9. Assess VF
- 10. Perform anterior chamber OCT
- 11. Measure IOP at 10:00 a.m. (\pm 30 minutes)
- 12. Measure IOP at 4:00 p.m. (±30 minutes)
- 13. Perform dilated funduscopic exam
- 14. Perform body system assessment (can be performed anytime during the site visit)
- 15. Assess vital signs (can be performed anytime during the site visit)

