- 12. Assess vital signs only at Visit 16/Month 12 and Visit 19/Month 15 (can be performed anytime during the site visit)
- 13. Perform dilated funduscopic examination only at Visit 16/Month 12
- 14. Collect non-fasting blood and urine for clinical laboratory tests only at Visit 16/Month 12
- 15. Collect used timolol maleate 0.5% ophthalmic solution bottle and distribute new bottle to patient

Patients are expected to remain in the clinic for the completion of all procedures (\sim 7:30 a.m. to \sim 9:00 a.m.).

Before patients leave the clinic, they should receive an appointment for their next study visit and the instructions provided in Section 12.3.4.

12.12. Visit 22/Month 18 ± 7 Days/Treatment Period Study Exit, Cohort 2 **Extension 1 (if patient chooses not to enroll in Extension 2)**

If a patient discontinues prior to the Visit 22/Month 18, or declines to continue into the Cohort 2 Study Extension 2 the following procedures are to the performed. If the patient chooses to continue into the Cohort 2 Study Extension 2, please follow the procedures in Section 12.13.

Query patient about changes in concomitant medications and whether or not they have experienced symptoms suggesting an AE. AEs will be documented.

- 1. Assess BCVA (ETDRS) with manifest refraction
- 2. Perform pupil measurement
- 3. Perform slit lamp biomicroscopy
- 4. Perform corneal staining
- 5. Measure IOP at 8 am (±30 minutes, please make sure that timolol maleate 0.5% ophthalmic solution is administered after the IOP measurement)
- 6. Perform gonioscopy (if gonioscopy images are collected, please conduct the gonioscopy after the 4:00 p.m. IOP measurement)
- 7. Perform pachymetry (contact)
- 8. Perform specular microscopy (non-contact) for both eyes (can be performed anytime during the visit)
- 9 Assess VF
- 10. Perform anterior chamber OCT with the ENV515 implant(s) in the field of view of at least one OCT image
- 11. Measure IOP at 10:00 a.m. (±30 minutes)
- 12. Measure IOP at 4:00 p.m. (±30 minutes)
- 13. Perform dilated funduscopic exam
- 14. Perform body system assessment (can be performed anytime during the site visit)
- 15. Assess vital signs (can be performed anytime during the site visit)
- 16. Collect non-fasting blood and urine for clinical laboratory tests and systemic PK
- 17. If female of childbearing potential, perform urine pregnancy test
- 18. Collect used timolol maleate 0.5% ophthalmic solution bottle
- 19. Complete the exit form

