15.1.11. Intraocular Pressure

All IOPs will be measured with a Goldmann applanation tonometer. The calibration of the tonometer will be checked at least monthly and recorded in a log. Diurnal curves will be recorded at specified visits. The time of tonometry will be recorded on the source document for all visits.

IOP should be measured only after the biomicroscopic exam is completed and must be measured prior to pupil dilation. Measurements will be taken by two qualified independent study site personnel using a Goldmann applanation tonometer affixed to a slit lamp with the patient seated. One person will adjust the dial in masked fashion and a second person will read and record the value. The patient and slit lamp should be adjusted so that the patient's head is firmly positioned on the chin rest and against the forehead rest without leaning forward or straining. Both eyes will be tested, with the right eye preceding the left eye. Each IOP measurement is to be recorded.

One person ("the measurer") looks through the binocular viewer of the slit lamp at low power. The tension knob is pre-set at a low pressure value (4 to 6 mmHg). The measurer follows the image of the fluorescein-stained semicircles while he/she slowly rotates the tension knob until the inner borders of the fluorescein rings touch each other at the midpoint of their pulsation in response to the cardiac cycle. When this image is reached, the measurer takes his/her fingers off the tension knob and the second person ("the reader") records the IOP reading along with the date and time of day in the source document, thus maintaining a masked IOP reading.

For Cohorts 1 and 2, three consecutive measurements will be taken to determine IOP in the manner described above. All three measurements will be recorded and the median IOP of the three measurements will be recorded and used in the analysis.

For Cohort 3, only two measurements are necessary if the pressure measurements are the same. If the two measurement are not identical, a third measurement is required.

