16.2. Concomitant Medications

16.2.1. Permitted Medications

Medications permitted include systemic medications with the exception of oral, ocular, or IV steroids. Only non-preserved artificial tears will be allowed to be administered as an ocular treatment. Medications not specifically excluded in Section 16.2.2 may be taken as necessary.

The use of topical non-steroidal anti-inflammatory agents (e.g. PROLENSA, ACULAR, ILEVRO or others) is allowed per the discretion of the investigator for 1 to 2 days prior to and 7 days immediately following ENV515-3-2 administration via intracameral injection.

All medications taken by a patient 30 days prior to Visit 1 through the end of the study will be recorded in the eCRF and the patient's medical chart. **This includes all ocular medications given on the day of dosing.** The generic name (if known, otherwise the trade name) of the drug, dose, route of administration, duration of treatment (including start and stop dates), frequency, and indication will be recorded for each medication.

Topical medications that are administered to all patients as part of conducting safety assessments or routine procedures are not required to be recorded in the eCRF. For example, topical medications used for the following are not required to be recorded in the eCRF:

- Dilating agents
- Anesthesia
- Staining (i.e., fluorescein)

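### Cohort 2 exit lists put visual field, with dilation for small pupils, before the 10 a.m. and 4 p.m. IOP; at image-collecting sites in Cohorts 2 and 3, gonioscopy changes place between Baseline and post-dose diurnal visits

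*Protocol*

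**What the plan says.** On tonometry, Protocol 15.1.11 states: "IOP should be measured only after the biomicroscopic exam is completed and must be measured prior to pupil dilation". On perimetry, 15.1.10 states: "The pupil should be at least 3 mm in diameter. If not, pharmacologic dilation should be used for VF testing".

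The Cohort 2 exit lists (12.10 at Month 12, 12.12 at Month 18, 12.14 at Month 21) share one numbering. The 8 a.m. IOP is step 5 and visual field is step 9. Then come "11. Measure IOP at 10:00 a.m. (±30 minutes" and "12. Measure IOP at 4:00 p.m. (±30 minutes". The dilated fundus examination is step 13.

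On gonioscopy, 15.1.9 says that selected sites in Cohorts 2 and 3 take photographs, starting at Visit 5, and adds: "If gonioscopy images are collected, please conduct the gonioscopy after the last IOP measurement". The post-dose diurnal lists repeat this by moving gonioscopy after the 4 p.m. IOP when images are taken. The Baseline lists (12.2.1 and 13.2) have no such condition and place gonioscopy between the 8 a.m. and 10 a.m. IOP.

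On use of the readings, the Cohort 2 synopsis names time-matched change at Days 14, 42 and 84 as primary, and Section 10 names change in mean diurnal IOP after Day 84. The 2019 SAP (8.1) says that IOP is collected at 8 a.m., yet summarises it by visit, time and eye against a time-matched baseline. Its Table 14.2.1 is by visit and time point.

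**The concern.** A time-matched change isolates treatment only if the reading at a given clock time is taken under the same conditions at baseline and follow-up. The protocol protects the diurnal curve from dilation by placing every dilated fundus examination after the 4 p.m. reading. Visual field at the Cohort 2 exits is a gap in that protection. A site with a patient whose pupil is under 3 mm must either break 15.1.11 or depart from the list.

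The gonioscopy issue is different. No rule is broken, but at imaging sites the 10 a.m. and 4 p.m. readings follow a contact examination at Baseline and precede it after dosing. Any effect of that examination on IOP would then appear as change from baseline, and it would vary with whether the site takes photographs. The SAP has no flag or split for either situation.

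**Working it through.** The plan states no figure on this point, so there is nothing to reproduce. The check sets the step numbers side by side. An asterisk means that gonioscopy moves after the 4 p.m. IOP if images are taken.

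| Visit (Protocol section) | 8 a.m. IOP | Gonioscopy | Visual field | 10 a.m. IOP | 4 p.m. IOP | Dilated fundus |
|---|---|---|---|---|---|---|
| Cohort 2 Baseline (12.2.1) | 5 | 6 | none | 10 | 13 | 14 |
| Cohort 2 Day 14 (12.5) | 4 | 5* | none | 8 | 9 | none |
| Cohort 2 Day 42 (12.7) | 4 | 5* | none | 8 | 9 | none |
| Cohort 2 Day 84 (12.8) | 5 | 6* | none | 10 | 11 | 14 |
| Cohort 2 exits (12.10, 12.12, 12.14) | 5 | 6* | 9 | 11 | 12 | 13 |
| Cohort 3 Baseline (13.2) | 6 | 7 | none | 12 | 14 | 15 |
| Cohort 3 Day 84 (13.8) | 5 | 6* | none | 10 | 11 | 14 |

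**Exposure to visual field.** A Cohort 2 patient has 3 (Visits 5, 6, 7) + 8 (Visits 8 to 15) + 1 (exit) = 12 post-dose diurnal visits, so 12 × 2 = 24 readings per eye at 10 a.m. or 4 p.m. Two of the 24 (8.3%) follow visual field. Patients who continue at Month 12 or Month 18 have neither visual field nor 10 a.m. and 4 p.m. readings at that visit (Tables 3 and 4), so there is one exposed exit per patient. With five patients that is at most 5 visits, or 5 × 2 = 10 readings per eye, and only where the pupil is under 3 mm. None of the 8 a.m., Day 14, Day 42 or Day 84 readings is exposed. The Cohort 3 exits take only an 8 a.m. IOP, before visual field.

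**Exposure to the gonioscopy change.** At an imaging site it reaches all 24 of these readings in Cohort 2. In Cohort 3 there are 4 (Visits 5, 5a, 6, 7) + 5 (Visits 8 to 12) = 9 post-dose diurnal visits, so 18 readings per eye. At other sites it reaches none. Cohort 2 had two sites (1.5.1); how many took images is not stated.

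**Size.** Let d be the shift in mmHg from the preceding procedure. The documents do not give it, so d = 1 to 3 is an assumption, and d need not be the same for dilation and gonioscopy. With two of three readings shifted, an eye's diurnal mean moves by 2d/3. With k of five patients affected, a single time-point mean moves by kd/5 and the mean diurnal value by 2kd/15.

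| d (assumed) | One eye, diurnal mean | k = 1: time point / diurnal | k = 5: time point / diurnal |
|---|---|---|---|
| 1 | 0.67 | 0.2 / 0.13 | 1.0 / 0.67 |
| 2 | 1.33 | 0.4 / 0.27 | 2.0 / 1.33 |
| 3 | 2.00 | 0.6 / 0.40 | 3.0 / 2.00 |

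These are upper values for each d, because they carry the full shift through to 4 p.m. For visual field, k counts dilated patients, with all five taken to exit at the same visit. For gonioscopy, k counts patients at imaging sites, and the shift sits in the baseline instead of the follow-up.

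**The case against.** The best reply is that the lists may not bind. The Cohort 2 Baseline list is described as a general order, and the exit lists as supplied carry no ordering sentence (possibly lost in text extraction). A careful site would let 15.1.11 prevail and defer the visual field. That is plausible, but the text leaves it to the site, and nothing in the analysis would show what was done.

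It is also fair that little rests on the exposed exit readings. The extension efficacy measures use 8 a.m. IOP, the 2019 SAP names 8 a.m., and no testing is planned. If Table 14.2.1 shows only 8 a.m. values, neither issue reaches it. Its title and the wording of SAP 8.1 leave open that 10 a.m. and 4 p.m. will appear.

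Some stronger readings are tempting but not supported:

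- **That diurnal change is unmatched in general.** Visual field never precedes a primary reading on the same day, 8 a.m. readings keep their place throughout, and non-imaging sites keep the same gonioscopy order.
- **That the Cohort 1 primary endpoint is compromised.** When dilation is needed for visual acuity, "the assessment should be performed after the slit lamp biomicroscopy and IOP measurement" applies at both Visit 2 and Visit 8. It does not say after the 8 a.m. reading only, and 15.1.11 governs it. Gonioscopy is step 6 at both visits.
- **That affected readings cannot be identified.** Section 16.2.1 lists "Dilating agents" among items that need not enter the eCRF, but as an example of topical agents given to all patients. Pupil size is measured at step 2 of each exit list and appears in the SAP listings, and source records can be checked.

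**Conclusion.** The point holds in a narrow form. There is a direct conflict between the Cohort 2 exit lists read with 15.1.10 and the rule in 15.1.11, confined to patients with a pupil under 3 mm and to at most five visits. There is also a baseline-to-follow-up difference in procedure order at imaging sites in Cohorts 2 and 3. This second part reaches the 10 a.m. and 4 p.m. changes on Days 14, 42 and 84.

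Neither the frequency of small pupils, nor the number of imaging sites, nor the IOP shift can be taken from the documents. One dilated patient in five would move the exit diurnal mean by 0.13 to 0.40 mmHg for an assumed d of 1 to 3. The gonioscopy effect ranges from zero, if no site took images or the examination has no effect, up to 2d/3 if every patient was at an imaging site. A shift equal in both eyes would cancel from a study-eye versus fellow-eye difference, but the 2019 SAP reports change by eye.

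This is an avoidable inconsistency that is worth correcting. It does not show that the IOP results are biased, and it does not justify restricting the analysis to 8 a.m.

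**What to change.** **Protocol text.** Reconcile 12.10, 12.12 and 12.14 with 15.1.11 by listing visual field after the 4 p.m. IOP; placing it directly after keeps it ahead of the dilated fundus examination, as now. At Baseline and every post-dose diurnal visit, at all sites, list gonioscopy after the last IOP reading.

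**Data already collected.** For the at most five Cohort 2 exit visits, use the recorded pupil measurement as a first screen, then check source records for dilation and its time. The time is needed because the dilated fundus examination falls on the same day. Flag in Table 14.2.1 any 10 a.m. or 4 p.m. reading taken after dilation. State in SAP 8.1 which time points the table contains. If 10 a.m. and 4 p.m. are included, show their changes separately for imaging and non-imaging sites, descriptively.

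**Cost.** A slightly longer end of visit, a small source check and one extra split of a descriptive table. With groups this small the split will be imprecise and serves only to show whether the two kinds of site look alike.
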